2.2 Study Rationale

OAB is recognized by the International Children's Continence Society (ICCS) [Austin et al, 2014], this study is intended to assess the effects of mirabegron in pediatric patients with OAB to understand its potential role in therapy. This study (Study 178-CL-204) is part of the sponsor's clinical program to develop mirabegron for OAB in pediatric subjects. In the EU, the development of mirabegron for the indication of OAB is outlined in the pediatric investigational plan (PIP) for mirabegron and has been approved by the Pediatric Committee. This study is part of PIP commitment.

2.3 Risk-Benefit Assessment

This study will be conducted as a double-blind, randomized, multicenter, parallel group, placebo-controlled sequential dose titration study in pediatric subjects from 5 to < 18 years of age with OAB.

The study design and dose rationale are presented in [Section 4 Study Design and Dose Rationale].

Mirabegron tablets have been approved for the indication of OAB in adult subjects. Mirabegron oral suspension has been shown to be safe and well tolerated in 2 phase 1 studies in healthy adult subjects (Studies 178-CL-201 and 178-CL-208). In the pediatric phase 1 studies executed thus far, mirabegron tablets and mirabegron oral suspension had an acceptable safety profile and were well tolerated. Given the available data on mirabegron in the adult population and in the pediatric population to date, the risk-benefit attributes are well defined and can be managed through ongoing safety assessments throughout study conduct as defined in the Schedule of Assessments [Table 1].

The important identified and potential risks in adults are recognized as potential drug safety risks for this study (Study 178-CL-204). These risks will be monitored on a regular basis and can be mitigated as follows:

 The initial dose of mirabegron will be based on the subject's body weight and is predicted to achieve plasma concentrations equivalent to the steady-state exposures Sponsor: APGD ISN/Protocol: 178-CL-204 EudraCT number 2016-001767-37

- CONFIDENTIAL -

expected with 25 mg mirabegron administered once daily in adults (PED25). This low dose is chosen considering possible beta-adrenergic side effects of mirabegron.

- At visit 5/week 4 (i.e., after 4 weeks on PED25), dose up-titration to PED50 will be performed unless the investigator determines that the subject is adequately treated for OAB at the PED25 dose or if there are safety concerns identified and considered associated with the use of PED25. Dose down-titration from PED50 to PED25 can be done at any time thereafter for safety reasons. By striving to get an efficacious dose of mirabegron early after start of dosing, the risk for bladder and kidney damage is mitigated.
- Potential fetal disorders after exposure during pregnancy is mitigated by the inclusion criteria
- Hypersensitivity reactions (immediate or nonimmediate and cutaneous or noncutaneous) will be monitored by AE monitoring and will require discontinuation of study treatment
- Potential UTI will be monitored by urinalysis at each visit in the clinic
- Increased blood pressure will be monitored by at-home and clinic measurements and can be mitigated by dose titration
- Increased heart rate and tachycardia will be monitored by at-home and clinic measurements and can be mitigated by dose titration
- Potential QT prolongation will be monitored by ECG at each visit at the clinic and can be mitigated by dose titration
- Potential events by concomitant treatment with CYP2D6 substrates with narrow therapeutic index is mitigated by excluding these medications

For activation of thermogenesis in brown fat, weight loss will be monitored by regular body weight measurements and the potential activation of thermogenesis will be monitored by body temperature measurements.

For both the tablet and the oral suspension formulation, all excipients are pharmaceutical grade materials and are considered safe for the intended pediatric population. Their concentrations remain below the acceptable daily intake as set by the joint Food and Agriculture Organization (FAO) of the UN and the WHO (joint FAO/WHO Expert Committee on Food Additives, 2015).

The protocol is designed to monitor safety and mitigate risk to the pediatric subject by optimizing the number of vital signs, ECG and post void residual (PVR) volume assessments, minimizing the number of blood draws (safety and pharmacokinetic sampling) and focusing the number of study visits.

The use of population pharmacokinetics for the analysis of the pharmacokinetic profile of mirabegron allows reduction of the number of blood draws for pharmacokinetic analysis to 2. Butterfly needles can be used and are allowed to stay in place to reduce the number of punctures.

The blood draws for clinical laboratory tests have been minimized to lessen subject burden while ensuring subject safety. Additional hematology and biochemistry tests will be performed at visit 3/week 0 (baseline) and visit 8/week 14 (end of study [EoS]) only if an AE

11 Feb 2021 Astellas Page 31 of 157

Sponsor: APGD ISN/Protocol: 178-CL-204 EudraCT number 2016-001767-37

- CONFIDENTIAL -

related to hematology, biochemistry or urinalysis parameters occurred since the previous visit or at the discretion of the investigator.

The assessments to be performed are routine assessments and generally do not pose any particular risk to the subjects. Every effort will be made to reduce the anxiety felt by subjects, e.g., during a blood test, topical anesthetic will be offered at venipuncture to minimize distress of the subject.

Subjects may experience AEs associated with the assessments performed during the study, such as local irritations due to ECG recording, and bleeding, hematoma as a result of blood collection, or the experience of transient stinging or burning during emptying or of the passing of a little blood as a result of the urodynamic investigation. There is also a small risk of developing a bladder infection in relation to the urodynamic procedure.

An independent Data and Safety Monitoring Board (DSMB) will be established [Section 10.4 Study Organization]. A separate charter will describe the responsibilities of the DSMB.

3 STUDY OBJECTIVE(S) AND ENDPOINT(S)

The primary, secondary and exploratory objectives and endpoints for this study are listed in [Table 5]. Primary and secondary objectives and endpoints apply to children only; exploratory objectives and endpoints also apply to adolescents.

Table 5 Study Objectives and Endpoints

| Objectives | Endpoints |
|---|--|
| Primary | |
| • To evaluate the efficacy of mirabegron in children (5 to < 12 years of age) with OAB | Change from baseline at the end of the 12-week treatment period: Mean number of micturitions per 24 hours |
| Secondary | 1 |
| To evaluate the efficacy of mirabegron in children (5 to < 12 years of age) with OAB | Change from baseline at the end of the 12-week treatment period: |
| | Mean volume voided per 24 hours |
| | Maximum volume voided |
| | Mean number of daytime incontinence episodes per 24 hours |
| | Mean number of nighttime incontinence episodes per 24 hours |
| | Mean number of daytime micturitions per 24 hours |
| | • Number of dry (incontinence-free) days per 7 days at the end of the 12-week treatment period |
| Table continued on next page | |

Sponsor: APGD ISN/Protocol: 178-CL-204

EudraCT number 2016-001767-37

- CONFIDENTIAL -

| Objectives | Endpoints |
|--|---|
| To evaluate the safety and tolerability of mirabegron in pediatric subjects with OAB | Nature, frequency and severity of AEs Clinical laboratory tests (hematology, biochemistry and urinalysis) Vital signs (blood pressure and pulse) Routine 12-lead ECG PVR volume Acceptability and palatability questionnaire |
| To evaluate the pharmacokinetics after multiple dose administration of mirabegron in pediatric subjects with OAB | Steady-state C _{max} , AUC _{tau} , C _{trough} , T _{max} , CL/F and Vz/F. Additional parameters may be calculated based on the population pharmacokinetic model used |
| Exploratory | |
| To evaluate the efficacy of mirabegron in pediatric subjects (5 to < 18 years) with OAB | Percentage of subjects with a reduction in daytime incontinence episodes (< 50% reduction [nonresponder], 50% [partial responder] and 100% [responder]) Improvement from baseline in worst incontinence grading Change from baseline at the end of the 12-week treatment period adjusted for fluid intake: Mean number of micturitions per 24 hours Change from baseline at the end of the 12-week treatment period (adolescents only): Mean number of micturitions per 24 hours Mean number of daytime micturitions per 24 hours Mean volume voided per 24 hours Mean number of incontinence episodes per 24 hours Number of dry (incontinence-free) days per 7 days at the end of the 12-week treatment period (adolescents only) Mean number of daytime grade 3 or 4 (PPIUS) urgency episodes per 24 hours (adolescents only) |

AE: adverse event; ECG: electrocardiogram; OAB: overactive bladder; PPIUS: patient perception of intensity of urgency scale; PVR: post void residual.

3.1 Estimand

The estimand of most clinical importance for this study is defined by the following 4 attributes:

- Target population: all children who took at least 1 dose of the study drug, and in whom a nonmissing measurement for micturition frequency at baseline and after administration of the study drug is available
- Outcome measurement: micturition frequency/day (24 hours)
- Intercurrent events:
 - 1. Discontinuation from treatment (if week 12/EoT not obtained)
 - 2. AE UTI (if occurred in week 12/EoT)

Sponsor: APGD ISN/Protocol: 178-CL-204

EudraCT number 2016-001767-37

- CONFIDENTIAL -

3. Other muscarinic antagonists or botulinum toxin see [Appendix 12.6 List of Excluded Concomitant Medications]) (if taken during the last 2 weeks prior to week 12/EoT assessment); in all cases, a hypothetical strategy will be applied

• Population-based summary: Change from baseline to week 12/EoT in micturition frequency/day (= primary endpoint, primary estimator), compared to placebo

For this placebo-controlled study, this "de jure" estimand chosen is considered the appropriate choice. As some effect is expected early in the study and with continued treatment could be expected to be maintained, it's considered appropriate to impute for subjects with missing values at visit 7/week 12/EoT by their last recorded post baseline visit value prior to it. This strategy also assumes that the responses after the intercurrent event would be same as for patients continuing on their respective treatment.

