At visit 3/week 0 (baseline) inclusion and exclusion criteria will be evaluated. Subjects continuing urotherapy who still meet the OAB entry criteria at baseline will be randomized. Subjects whose symptoms are not satisfactorily controlled with urotherapy and still fulfill the inclusion/exclusion criteria will enter the study. These subjects will be randomized to receive mirabegron in pediatric equivalent dose 25 mg (PED25) or placebo using a 1:1 ratio. Subjects with a body weight of \geq 35 kg are to receive the tablet unless unable to swallow tablets and would be provided the oral suspension as an alternative. Subjects with a body weight < 35 kg or those who cannot be dosed with the tablet will receive an oral suspension. Daily investigational product (IP) administration will start on day 1 (i.e., the day after this visit) and continue at this dose until visit 5/week 4 (i.e., for 4 weeks). Urotherapy will continue throughout the study treatment period until visit 7/week 12 (EoT).

At visit 5/week 4, dose up-titration to mirabegron in pediatric equivalent dose 50 mg (PED50) will be performed unless the investigator determines that the subject is adequately treated for OAB at the PED25 dose or if there are safety concerns identified and considered associated with the use of PED25. Dose down-titration from PED50 to PED25 can be done at any time thereafter for safety reasons.

Subjects will start with the subsequent 7-day bladder e-diaries approximately 7 days prior to the indicated visit (or TC).

Pharmacokinetic blood samples will be collected at visit 5/week 4 and visit 7/week 12 (EoT) as indicated in the Schedule of Assessments.

- CONFIDENTIAL -

• Follow-up period (2 weeks):

This period starts the day after visit 7/week 12 (EoT) and ends with visit 8/week 14 (end of study [EoS]). The follow-up period is applicable to all subjects who have been randomized and received IP.

ISN/Protocol: 178-CL-204

At visit 7/week 12 (EoT), IP administration will be stopped and a safety observation period of 2 weeks will start.

An independent Data and Safety Monitoring Board (DSMB) will be established. A separate charter will describe the responsibilities of the DSMB.

The IP will not be provided after study completion without written approval from the sponsor.

Inclusion/Exclusion Criteria:

Inclusion Criteria

Subject is eligible for the study if all of the following apply:

Inclusion at Visit 1/Week -4 (Screening)

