9.1 Sample Size

Efficacy of mirabegron in children will be based on both primary and secondary endpoints. Given the clinical hurdle to demonstrate efficacy in a population challenging to recruit, an alpha-level of 10% would appear reasonable and justified. In a study with propiverine in children, Marschall-Kehrel (2009) showed a difference in mean number of micturition episodes/24 hours of 0.8 between propiverine and placebo, with a SD between 2.2 and 2.3. Assuming at least similar efficacy of mirabegron, with a treatment effect of 0.9 micturitions per day between mirabegron and placebo and a common SD of 2.3, a sample size of 82 evaluable subjects (children) per treatment group is assumed per treatment group would provide a power of 80%.

These assumptions, together with levels for Type-1 error and power were agreed upon with Pediatric Committee in the current Pediatric Investigation Plan.

Under the assumption that after randomization about 10% of the subjects will not be evaluable for the analysis of the primary endpoint (i.e., not fulfilling the criteria for inclusion in full analysis set [FAS]), at least 184 children (5 to < 12 years of age) must be randomized in order to have at least 164 evaluable children for the analysis of the primary efficacy endpoint.

For adolescents, no formal sample size will be calculated; at least 32 adolescents (12 to < 18 years of age) must be randomized, yielding at least 16 adolescents on mirabegron. Further assuming a 50% screen failure rate, approximately 368 children have to be enrolled to achieve 184 children (5 to < 12 years of age) randomized and approximately 64 adolescents will be enrolled to achieve at least 32 adolescents (12 to < 18 years of age) randomized (at least 92 children and 16 adolescents must be randomized to mirabegron).

Recruitment will continue until the minimum number to be randomized in both children and adolescents have been achieved.

11 Feb 2021 Astellas Page 58 of 157

ISN/Protocol: 178-CL-204

9.2 **Analysis Sets**

Detailed criteria for analysis sets will be laid out in classification specifications and the allocation of subjects to analysis sets will be determined prior to database hardlock.

9.2.1 **Full Analysis Set**

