9.4.1 Analysis of Primary Endpoint

9.4.1.1 Primary Analysis

The primary estimator for the primary estimand as defined in [Section 3.1 Estimand] will be calculated according to the evaluation of the primary efficacy endpoint. The primary efficacy endpoint change from baseline to week 12/EoT in mean micturitions per 24 hours (in children [5 to < 12 years of age]), will be analyzed using an analysis of covariance (ANCOVA). The ANCOVA model will include treatment group, sex and geographical region as fixed effects and the mean number of micturitions per 24 hours at baseline as covariate. This analysis will be performed and once with imputation of missing week 12 data using the last observation carried forward (LOCF) method.

The hypothesis for comparisons is given as follows:

H0: The adjusted mean change from baseline at week 12 in mean number of micturitions per 24 hours for mirabegron and placebo are the same.

H1: The adjusted mean change from baseline at week 12 in mean number of micturitions per 24 hours for mirabegron and placebo are not the same.

Statistical testing will be done at a 2-sided 0.1 significance level. A 90% CI for the treatment difference (mirabegron – placebo) will be provided. The primary analysis will use the FAS. The plausibility of the underlying assumption of missing at random for the primary estimator will be evaluated, and; therefore, the estimation of the treatment effect. Sensitivity analyses under alternative assumptions for missing data mechanisms such as missing not at random to show robustness of the estimates will be further specified in the SAP.

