9.4.1.2 Secondary Analysis

The same analysis of the primary endpoint as described in [Section 9.4.1.1 Primary Analysis] will be conducted using the PPS, and without imputation using FAS.

The change from visit 3/week 0 (baseline) to visit 7/week 12 (EoT) in mean number of micturitions per 24 hours in children (5 to < 12 years of age) will be analyzed. The primary analysis for the primary endpoint will be using a repeated measures ANCOVA model with treatment group, visits (week 4, 8 and 12), sex, geographical region and the interaction between treatment group and visit as fixed effects and mean number of micturitions per 24 hours at baseline as covariate. Mirabegron will be compared to placebo using a linear

Sponsor: APGD ISN/Protocol: 178-CL-204

contrast within the repeated measures ANCOVA model, with 2-sided significance level of alpha = 0.1 and 90% CI. This analysis will be conducted using the FAS.

In addition to the parametric ANCOVA, a nonparametric ANCOVA will also be performed: (stratified) rank ANCOVA. This analysis will be conducted using the FAS.

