6.4.1.1 Primary Analysis for Primary Efficacy Endpoint

The primary estimator for the primary estimand as defined in Section [2.1.1 Estimand] will be calculated according to the evaluation of the primary efficacy endpoint. The primary efficacy endpoint will be analyzed using an analysis of covariance (ANCOVA). The ANCOVA model will include treatment group, sex and geographical region as fixed effects and the mean number of micturitions per 24 hours at baseline as covariate. This analysis will be performed with imputation of missing visit 7/week 12 data using the last observation carried forward (LOCF) method.

The hypothesis for comparisons is given as follows:

- H₀: The adjusted mean change from baseline at visit 7/week 12 in mean number of micturitions per 24 hours for mirabegron and placebo are the same.
- H1: The adjusted mean change from baseline at visit 7/week 12 in mean number of micturitions per 24 hours for mirabegron and placebo are not the same.

Statistical testing will be done 2-sided at a 10% significance level. A 90% CI for the treatment difference (mirabegron – placebo) will be provided. The primary analysis will use the FAS. The plausibility of the underlying assumption of missing at random for the primary estimator will be evaluated and, therefore, the estimation of the treatment effect.

The ANCOVA model results will be presented with least squares (LS) means and two-sided 90% confidence intervals (CIs) for mean changes from baseline within each treatment group. Differences in LS means between mirabegron versus placebo will be derived and presented together with two-sided 90% CIs. T-statistics corresponding to the Type III sums of squares for the differences in the LS means will be used to obtain p-values for the comparisons.

Model fitting will be visually assessed. A scatter plot of residuals versus predicted values, along with histogram and normal probability plots will be produced.

Sensitivity analyses under alternative assumptions for missing data mechanisms such as missing not at random to show robustness of the estimates will be further specified.

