6.4.1.3.3 Analysis using Repeated Measures ANCOVA

The primary endpoint will also be analyzed using a repeated measurements analysis of covariance (ANCOVA) model with treatment group, visit (week 2, 4, 8 and 12), sex, geographical region and the interaction between treatment group and visit as fixed effects and mean number of micturitions per 24 hours at baseline as covariate.

An appropriate covariance structure will be selected for the within subject repeated measurements. An unstructured correlation pattern will be used to estimate the variance-covariance of the within-subject repeated measures at first instance. Parameters will be estimated using Restricted Maximum Likelihood with the Newton-Raphson algorithm and using the Kenward-Roger method for calculating the denominator degrees of freedom. If there is a convergence problem due to the unstructured covariance matrix, the unstructured covariance matrix will be replaced by the compound symmetry covariance matrix.

Mirabegron will be compared to placebo using a linear contrast within the repeated measurements ANCOVA model, with 2-sided significance level of alpha = 0.1 and 90% CI.

This analysis will be conducted on the FAS and will serve as a sensitivity analysis to the LOCF method used in the primary model to assess the robustness of the findings.

Model fitting will be visually assessed. A scatter plot of residuals versus predicted values, along with histogram and normal probability plots will be produced.

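### The primary LOCF analysis does not match the estimand's own assumption about children who stop, so the estimate can be biased and 80% power is not assured

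*Protocol*

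**What the plan says.** **Estimand.** Protocol 3.1 (also in the synopsis and SAP 2.1.1) applies a hypothetical strategy to three events: stopping treatment without a week 12 value, urinary tract infection at week 12, and recent use of antimuscarinics or botulinum toxin. A missing week 12 value is replaced by the last post-baseline one, on the ground that an early effect could be maintained with continued treatment. The section then adds: "This strategy also assumes that the responses after the intercurrent event would be same as for patients continuing on their respective treatment".

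**Primary analysis.** Protocol 9.4.1.1 specifies ANCOVA in the full analysis set (FAS): "This analysis will be performed and once with imputation of missing week 12 data using the last observation carried forward (LOCF) method". On the test it says: "Statistical testing will be done at a 2-sided 0.1 significance level". SAP 6.4.1.1 keeps LOCF and also states: "The plausibility of the underlying assumption of missing at random for the primary estimator will be evaluated".

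**Repeated measures model.** Protocol 9.4.1.2, headed as secondary analysis, says: "The primary analysis for the primary endpoint will be using a repeated measures ANCOVA model", with visits at weeks 4, 8 and 12. SAP 6.4.1.3.3 uses weeks 2, 4, 8 and 12 and gives the model another role: it "will serve as a sensitivity analysis to the LOCF method used in the primary model".

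**Dose.** The synopsis says: "At visit 5/week 4, dose up-titration to mirabegron in pediatric equivalent dose 50 mg (PED50) will be performed". The exceptions are a child judged adequately treated on the lower dose, or a safety concern.

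**Sample size.** Protocol 9.1 plans 82 evaluable children per arm for 80% power, "with a treatment effect of 0.9 micturitions per day between mirabegron and placebo and a common SD of 2.3".

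**The concern.** Three descriptions of one estimator do not fit together. The estimand text says children who stop would respond like those who continue in their arm. The analysis text says missing at random. LOCF assumes that each child's own last value stays constant.

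The difference matters here because the dose changes on schedule. Diaries are kept in the week before weeks 2, 4, 8 and 12 (protocol 7.1.1), so under the schedule the week 2 and week 4 diaries reflect PED25. Children who continue mostly move to PED50, whose target exposure is 188 against 69 ng·h/mL (protocol 4.2), a ratio of 2.7. One post-baseline value is enough to enter the FAS, so a week 2 value can stand in for week 12. The argument from an early, maintained effect does not address the dose step.

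The choice also decides the trial. Protocol 9.10 and SAP 6.9 define a positive study by the primary efficacy analysis. The planned analyses that do match the stated assumption, repeated measures and multiple imputation under missing at random, have no part in that decision.

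**Working it through.** **Inputs from the documents:** difference 0.9, SD 2.3, 82 per arm, two-sided alpha 0.10; for the design scenario, changes of -1.8 on mirabegron and -0.9 on placebo (SAP Appendix 9.4).

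**Inputs assumed, because the documents give none:** *f*, the share of FAS children carried forward; *r*, the share of the week 12 difference present at the carried visit; *ρ*, the correlation between a child's last value and week 12.

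**1. The plan's own figure.** The standard error is 2.3 × √(2/82) = 0.359. Power is Φ(0.9/0.359 − 1.645) = 80.5% by the normal approximation and 80.2% by the noncentral t. The stated 80% reproduces. The figures below use the normal approximation.

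**2. Equal shares carried forward.** The expected LOCF difference is 0.9 × [1 − f(1 − r)].

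| f | r | Difference | Power |
|---|---|---|---|
| 5% | 0.5 | 0.878 | 78.8% |
| 10% | 0.5 | 0.855 | 76.9% |
| 20% | 0.5 | 0.810 | 72.9% |
| 10% | 0 | 0.810 | 72.9% |
| 10% | 1 | 0.900 | 80.5% |

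Power drops below 80% once f(1 − r) exceeds about 0.8%. If response is flat after the carried visit (r = 1), nothing is lost.

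**3. Unequal shares.** Suppose half of each arm's change is present at the carried visit: -0.9 on mirabegron, -0.45 on placebo.

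- 15% mirabegron, 5% placebo: arm means -1.665 and -0.8775, difference 0.788, power 70.8%.
- 5% and 10%: -1.755 and -0.855, difference 0.900, no bias.
- 5% and 15%: -1.755 and -0.8325, difference 0.923, power 82.2%, bias away from the null.

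**4. No true effect.** If both arms follow the placebo course, 5% against 20% carried forward gives a spurious 0.07 in favour of mirabegron (-0.8775 against -0.81) and a two-sided error rate of 10.6%.

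**5. The alternative estimator.** Under missing at random a repeated measures contrast at week 12 still targets 0.9, with an effective size of about 82 × [1 − f(1 − ρ²)] per arm. For f = 10% this gives 76.8% power at ρ = 0 and 78.7% at ρ = 0.7; for f = 20%, 72.5% and 76.7%. It removes the dilution but does not recover the missing information.

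**The case against.** **The size is unknown.** No share of missing week 12 values is stated. The 10% allowance in protocol 9.1 covers children outside the FAS, which is a different group. Protocol 8.1 and 8.2 encourage children who stop treatment to attend all visits, and four valid diary days suffice (SAP 5), so few may need carrying forward. This stands as a limit on magnitude, but it does not reconcile the texts.

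**The flat-response premise has some support.** Protocol 2.1.2.2 reports that the sponsor's pediatric study with PED25-to-PED50 titration showed improvement at week 4 that was sustained. That study was open-label and baseline-controlled, in neurogenic detrusor overactivity. It lends partial support only.

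**Power may be understated above.** The planned ANCOVA adjusts for baseline. At a difference of 0.855, an assumed correlation of 0.3 between baseline and change brings power back to 80.2%. The documents also do not say how missing data were handled in the propiverine study behind the planning effect. Both points are fair.

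**Matching analyses are already planned.** SAP 6.4.1.3 includes repeated measures, multiple imputation under missing at random and under missing not at random, and analysis without imputation. True; what remains is which one is primary.

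**Two primary analyses?** A reader might infer from protocol 9.4.1.2 that the trial has two. The section heading, the synopsis and the SAP all make the repeated measures model secondary or a sensitivity analysis. It is a wording slip, though one that needs correcting.

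**Conclusion.** The mismatch between estimand and estimator follows from the text alone and holds. LOCF carries out neither the stated assumption about continuing children nor missing at random, unless mean response is flat after the last diary. The default up-titration makes that doubtful for children last seen at week 2 or 4.

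A reader might go further and infer that the effect is biased, that 80% power is lost, or that the type I error is materially inflated. The documents do not support those statements. Direction and size depend on how many children are carried forward in each arm, from which visit, and on the time course in both arms. Bias can be toward the null, away from it, or zero; the error rate in the null scenario tried rises only from 10% to 10.6%. The illustrative 0.855 and about 77% power rest on equal 10% shares and half the effect at the carried visit, both assumptions. The sound conclusion is that the estimate can be biased and 80% is not assured.

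**What to change.** - Make the repeated measures ANCOVA of SAP 6.4.1.3.3 the primary estimator in the protocol synopsis, 3.1 and 9.4.1 and in SAP 2.1.1 and 6.4.1.1. It is not fully specified as it stands: name week 12 as the visit of the treatment contrast, and use one visit list (weeks 2, 4, 8, 12) in both documents. Keep the LOCF ANCOVA as a sensitivity analysis.
- Correct protocol 9.4.1.2 so that only one analysis is called primary.
- Make the futility model consistent. SAP 6.9 and Appendices 9.5 and 9.6 take means and SD from the LOCF ANCOVA; Appendix 9.4, section 2.2, uses a model with visit and treatment-by-visit terms.
- State the expected share of FAS children missing week 12, by arm if possible, and the power under it.

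If LOCF is kept as primary instead, the sentence on continuing children and the missing-at-random wording should go, and constancy after week 4 needs its own justification.

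**Cost.** Mostly wording, since both models are already planned on the same data and SAP 1 allows revision before hard lock. The futility formula needs more care: it is written for complete counts and a pooled ANCOVA SD. The primary result would then rest on missing at random and a covariance model, which the multiple-imputation analyses in SAP 6.4.1.3.5 already probe.
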